7.2 Site staff surveys schedule

Rev. Add3

Item	Baseline	12 - 15 months post Baseline Survey	Approximately 36 months post Baseline Survey
Baseline survey (Supplemental Appendix D)	Prior to first patient enrollment		
12-month survey (Supplemental Appendix E)		X	
36-month survey (Supplemental Appendix F)			After last patient is enrolled
Focus Group Interview			To be held after initiation of 36 month survey collection

Rev. Add4

7.3 Randomization groups schedule (approximate)

	Week	EUC (Control)	VIT (Intervention)
Randomization	0	Quitline referral email	TeleHealth test call
Month 1	1		Session 1 + 1st medication fill
	2		Session 2
	3		Session 3
	4		Session 4
Month 2	5		Session 5 + 2nd medication fill
	6		Session 6
	7		
	8		
Month 3	9		Session 7 + 3rd medication fill
	10		Session 8 + 3 month follow-ups
	11		
	12	3 month follow-ups	
Month 4	13		Session 9
	14		
	15		
	16		
Month 5	17		Session 10

	Week	EUC (Control)	VIT (Intervention)
	18		
	19		
	20		
Month 6	21		Session 11 + 6 month follow-ups
	22		
	23		
	24	6 month follow-ups	
Study completion			Exit interviews

Rev. Add2

7.4 Data collection schedule during eligibility screening, recruitment, and enrollment

	Pre-screen 	Step 0 	Step 1 	Step 2 
Sex 		X		
Age* 		X		
Race 		X		
Ethnicity 		X		
Language* 	X	X		
Cancer diagnosis* 		X		
Cancer stage 		X		
Date of diagnosis* 	X	X		
Smoking status* 	X	X		
Care at NCORP site* 		X		
Email/web access* 	X	X		
ECOG PS* 	X			
Reasons for ineligibility 	X	X	X	
Reasons for refusal 	X	X	X	
Contact information 			X	
Randomization group				X

\* Characteristics from eligibility criteria

1. Will only be collected if the information is available
2. May be patient self-reported or pre-screened from medical records
3. Must be patient self-reported
4. This data will be transmitted via MSK REDCap survey.
5. This data will be entered in OPEN, RAVE and REDCap Enrollment Log.

7.5 Data collection schedule for patient enrollees (surveys)

	Baseline	3 Mo.	6 Mo.
Patient Enrollees			
Point-prevalence tobacco abstinence		X	X
Self-reported tobacco abstinence		X	X
Cigarettes per day	X	X	X
24-hr quit attempts		X	X
Sociodemographics	X		
Smoking history	X	X	X
Cancer variables	X		
Medical history	X		
Quality of life	X	X	X
Cancer and smoking beliefs	X	X	X
Physical symptoms	X	X	X
Environmental influences	X	X	X
Acceptability			X

7.6 Data collection schedule for site staff (surveys)

	Baseline	12 Month	36 Month
Site Staff			
Adoption	X	X	X
Appropriateness	X	X	X
Treatment fidelity	X	X	X
Cost		X	X
Feasibility	X	X	X
Site characteristics	X	X	X
Penetration/reach		X	X
Sustainability	X	X	X

Rev. Add3

. Site staff must complete baseline survey prior to first patient enrollment

Rev. Add4

. CCDR Leads will complete Site Characteristics at approximately 12 and 36 Month Follow-up (Appendices E and F)

## 8. Drug Formulation and Procurement

This information has been prepared by the ECOG-ACRIN Pharmacy and Nursing Committees.

### 8.1 Nicotine trans-dermal patch (NSC #5065)

#### 8.1.1 **Description**

Nicotine transdermal patches are supplied as transdermal patches for application to the skin containing nicotine as the active ingredient. The patches are available in dose concentrations of Nicotine 21mg delivered over 24 hours; Nicotine 14mg delivered over 24 hours; or Nicotine 7mg delivered over 24 hours.

Depending on specific commercial product, the patch may also contain the following inactive ingredients (not all inclusive) ethylene vinyl acetate-copolymer, polyisobutylene and high density polyethylene between clear polyester backings. Please refer to commercial package insert" as necessary.

#### 8.1.2 **Pharmacology**

Mode of Action:

Absorbed systemically; binds to nicotine receptors thereby reducing withdrawal symptoms (including nicotine craving) associated with smoking cessation.

Absorption: 68%

Duration: 24 hr

Peak plasma time: 8-9 hr

Peak plasma concentration: 5-17 ng/mL (average)

Elimination Half-life: 3-4 hr

Excretion: Urine

#### 8.1.3 **Storage and Stability**

Store at 20-25°C (68-77°F).

#### 8.1.4 **Administration**

See package insert for complete details for specific product used.

Dosing is determined by the number of cigarettes smoked daily when the patch is started.

>10 cigarettes per day **AND** weight >45 kg

- Start with the highest dose nicotine patch (21 mg/day) for six weeks, followed by 14 mg/day for two weeks, and finish with 7 mg/day for two weeks.

≤ 10 cigarettes per day **OR** weight < 45 kg

- Start with the medium dose nicotine patch (14 mg/day) for six weeks, followed by 7 mg/day for two weeks.

Patient is advised to pick "quit day" and begin using nicotine transdermal patches on that day and simultaneously stop smoking. They may continue to smoke if not immediately able to/willing to stop smoking, however every effort should be made to decrease the amount smoked while on replacement therapy, as continued smoking can increase adverse effects. It is important for patients to complete the full program, but some may need to use NRT for longer periods to keep from smoking.

Apply to clean, dry, non-hairy area of skin (typically upper arm or shoulder), being sure to rotate sight placed. Do not use the same sight for two consecutive applications. Try to not repeat any sight more than once in a 7 day period.

Apply new patch upon awakening and wear patch for 24 hours. In the event patient experiences vivid dreams or insomnia, remove patch before bedtime.

Do not cut patch, as this will result in uneven administration of medication and can increase risk of adverse effects and decrease efficacy.

After removing a patch, fold in half placing the sticky ends together, place in its original pouch, and discard out of the reach of children and pets. The patch still contains small amounts of nicotine which are poisonous children and pets.

#### 8.1.5

#### **Availability/How Supplied**

Nicotine transdermal patches are FDA approved for smoking cessation aid and are commercially available.

#### 8.1.6

#### **Side Effects**

There are no significant safety concerns associated with using more than 1 over-the-counter (OTC) nicotine replacement therapy (NRT) simultaneously or at same time as another nicotine-containing product (including cigarettes), however the potential for nicotine overdose is increased if patient continues to smoke. Every effort should be made to decrease the number of cigarettes smoked to zero while using replacement therapy.

Below are the most commonly reported adverse events related to nicotine transdermal patch. Please refer to the package insert/investigator's brochure for the comprehensive list of adverse events.

Gastrointestinal symptoms (nausea, vomiting, abdominal pain, diarrhea), headache, insomnia, vivid dreams, and application site irritation.

Contact your doctor if you experience these side effects and they are severe or bothersome.

The incidence of developing dependence on nicotine replacement is considered to be very low. Smokers may worry that they will become dependent on nicotine replacement, but nicotine dependence rarely

occurs. Nicotine replacement therapy has not been shown to increase or cause development of cancer.

Use of nicotine transdermal patches may not be appropriate in the following populations and should be carefully monitored by a physician

- non-smokers, occasional smokers, and children under 18 years of age (see Warnings),
- known hypersensitivity of the skin, allergy to nicotine or any patch components,
- generalized skin disorders,
- recovery phase of acute myocardial infarction, unstable or worsening angina pectoris, severe cardiac arrhythmias, and recent cerebrovascular accident.

Pregnancy and Breastfeeding:

Transdermal nicotine is considered US FDA Category D. The adverse effects on fetal and maternal health caused by cigarette smoking are clearly established. Nicotine freely passes into the placenta and is found in both amniotic fluid and umbilical cord blood (Luck & Nau, 1984; Hibberd et al, 1978). Nicotine is readily transferred to the fetus throughout pregnancy; the fetus is actually exposed to higher nicotine concentrations than the mother (Luck et al, 1985). The use of cigarettes or nicotine gum during the third trimester of pregnancy has been associated with diminished breathing movement in the fetus. There are no conclusive data to support different pregnancy categories for the various nicotine replacement therapy (NRT) products (Lyman & Raebel, 2001).

If you are pregnant or breast-feeding, only use this medicine on the advice of your health care provider. Smoking can seriously harm your child. Try to stop smoking without using any nicotine replacement medicine. This medicine is believed to be safer than smoking. However, the risks to your child from this medicine are not fully known."

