### 5.3 Virtual Intervention Treatment (VIT) (Arm B)

The VIT group will be offered up to 11 counseling sessions over approximately 6 months (approximate schedule: 4 weekly sessions through week 4; 4 biweekly sessions through week 12; and 3 monthly sessions through week 24) and up to 12 weeks of free FDA-approved combination NRT (patch and lozenge combined, or may elect to receive either option alone).

VIT participants will receive their 11 counseling sessions via MGH TeleHealth, which connects providers to patients through virtual HIPAA-compliant videoconferencing technology including: phone, video, email, mobile applications and remote monitoring. These virtual visits are conducted via a videoconference platform that addresses clinical privacy and security (e.g., Zoom, Doximity, or other HIPPA-compliant platform). Participants can use this videoconference platform on their computer, tablet or smartphone. The counseling will be delivered by a study-designated tobacco treatment coach based at MGH. Since the counseling takes place virtually, participants will be emailed handouts that are traditionally provided as hardcopies in person. These handouts, distributed at the end of Session 1, include a pill diary, 11 Reasons for Cancer Patients to Quit Smoking, and Health Benefits When You Quit Smoking.

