### 5.5.2 Terminology

- **Adverse Event (AE):** Any untoward medical occurrence associated with the use of an agent in humans [(in this protocol Nicotine Replacement Therapy (NRT)], whether or not considered agent related. Therefore, an AE can be **ANY** unfavorable and unintended sign (including an abnormal laboratory finding), symptom, or disease temporally associated with the use of a medicinal product, whether or not considered related to the medicinal product.
- **Attribution:** An assessment of the relationship between the adverse event and the protocol agent (NRT), using the following categories.

ATTRIBUTION	DESCRIPTION
Unrelated	The AE is clearly NOT related to the Nicotine Replacement Therapy (NRT)
Unlikely	The AE is doubtfully related to the Nicotine Replacement Therapy (NRT)
Possible	The AE may be related to the Nicotine Replacement Therapy (NRT)
Probable	The AE is likely related to the Nicotine Replacement Therapy (NRT).
Definite	The AE is clearly related to the Nicotine Replacement Therapy (NRT)

- **CTCAE:** The NCI Common Terminology Criteria for Adverse Events provides a descriptive terminology that is to be utilized for AE reporting. A grade (severity) is provided for each AE term.
- **Expectedness:** Expected events are those that have been previously identified as resulting from administration of the agent (NRT). An adverse event is considered unexpected, for expedited reporting purposes, when either the type of event or the severity of the event is NOT listed in the protocol (please refer to Section 8) or drug package insert.

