#### 8.1.7

#### Potential Interactions

There is increased risk of nicotine overdose in patients who continue smoking while using a nicotine replacement therapy, or those utilizing more than one form of nicotine replacement therapy. Caution should be used to prevent overdose, and smoking should be completely discontinued while using therapy.

Signs and symptoms of nicotine overdose may include:

abdominal or stomach pain, cold sweat, confusion, convulsions (seizures), disturbed hearing and vision, drooling, extreme exhaustion, pale skin, rapid heartbeat, and tremors. Contact your doctor if you experience any of these symptoms.

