#### 8.2.6 Side Effects

There are no significant safety concerns associated with using more than 1 over-the-counter (OTC) nicotine replacement therapy (NRT) simultaneously or at same time as another nicotine-containing product (including cigarettes), however the potential for nicotine overdose is increased if patient continues to smoke. Every effort should be made to decrease the number of cigarettes smoked to zero while using replacement therapy.

Below are the most commonly reported adverse events related to nicotine lozenge. Please refer to the package insert/investigator's brochure for the comprehensive list of adverse events.

Gastrointestinal symptoms (nausea, vomiting, abdominal pain, diarrhea, unpleasant taste), arthralgia, jaw pain, myalgia, dizziness, lightheadedness, headache, insomnia, hiccups

Contact your doctor if you experience these side effects and they are severe or bothersome.

The incidence of developing dependence on nicotine replacement is considered to be very low. Smokers may worry that they will become dependent on nicotine replacement, but nicotine dependence rarely occurs. Nicotine replacement therapy has not been shown to increase or cause development of cancer.

Use of nicotine polacrilex lozenges may not be appropriate in the following populations and should be carefully monitored by a physician:

- non-smokers, occasional smokers, and children under 18 years of age (see Warnings),
- known hypersensitivity of the skin, allergy to nicotine or any patch components,
- generalized skin disorders,
- recovery phase of acute myocardial infarction, unstable or worsening angina pectoris, severe cardiac arrhythmias, and recent cerebrovascular accident.

Pregnancy and Breastfeeding:

Nicotine Polacrilex is considered US FDA Category C. The adverse effects on fetal and maternal health caused by cigarette smoking are clearly established. Nicotine freely passes into the placenta and is found in both amniotic fluid and umbilical cord blood (Luck & Nau, 1984; Hibberd et al, 1978). Nicotine is readily transferred to the fetus throughout pregnancy; the fetus is actually exposed to higher nicotine concentrations than the mother (Luck et al, 1985). Nicotine use during the third trimester of pregnancy has been associated with diminished fetal breathing movements possibly due to decreased placental perfusion.

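### Section 8 is inconsistent on combined NRT and on smoking during NRT, and its lozenge precaution list is a copy of the patch list

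*Combined protocol and SAP*

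**What the plan says.** Section 5.3 offers Arm B up to 12 weeks of free NRT: "patch and lozenge combined, or may elect to receive either option alone". Under Section 5.3.2 a tobacco counselor discusses NRT at the first session and reviews contraindications with the decision trees in Appendices VII and VIII. The schedule in Section 7.3 places the first medication fill with Session 1.

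Section 8 describes each product under parallel headings.

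- **Combined use.** Side Effects (8.1.6 patch, 8.2.6 lozenge): "There are no significant safety concerns associated with using more than 1 over-the-counter (OTC) nicotine replacement therapy (NRT) simultaneously". Potential Interactions (8.1.7, 8.2.7) describes a raised risk of nicotine overdose in people who keep smoking on NRT, "or those utilizing more than one form of nicotine replacement therapy", and asks for caution.
- **Smoking during NRT.** Administration (8.1.4, 8.2.4) tells the patient to start the product on quit day and stop smoking then, but adds: "They may continue to smoke if not immediately able to/willing to stop smoking". Potential Interactions says: "smoking should be completely discontinued while using therapy".
- **Lozenge precautions.** Among the populations needing care with the lozenge, 8.2.6 lists "known hypersensitivity of the skin, allergy to nicotine or any patch components". The same words stand in the patch list in 8.1.6.

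**The concern.** Patch plus lozenge is the combination that Arm B is offered, so a sentence on combined use bears directly on the trial's treatment. One heading gives reassurance about combined use and the next warns of overdose.

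Smoking while on NRT is foreseeable by design. Section 5.3.1 sorts patients into three readiness branches, and two of them are for patients not yet ready to quit. NRT is nevertheless introduced at the first session for everyone.

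Under Section 5.3.2 counselors review contraindications and adjust the dose, the product is mailed, and notifying the oncology clinician before treatment was judged unnecessary. Staff therefore depend on the written text being consistent. What is at stake is the clarity of safety instructions, not a statistical property of the trial.

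**Working it through.** No arithmetic applies. The check sets the sections side by side.

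**1. Combined use**

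| Product | Side Effects | Potential Interactions |
|---|---|---|
| Patch | 8.1.6: no significant concern with more than one NRT product | 8.1.7: more than one form raises overdose risk; use caution |
| Lozenge | 8.2.6: same statement | 8.2.7: same warning |

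The sentence in 8.1.6 and 8.2.6 does carry a qualification, but it concerns only the patient who continues to smoke. The statement on combining products is left unqualified against the later warning. The mismatch occurs in both product sections.

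**2. Smoking during NRT**

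| Product | Administration | Potential Interactions |
|---|---|---|
| Patch | 8.1.4: stop on quit day; may continue if not able or willing to stop; reduce as far as possible | 8.1.7: stop completely while on therapy |
| Lozenge | 8.2.4: same | 8.2.7: same |

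Administration contains an explicit allowance. Potential Interactions contains none and does not refer back to it. This mismatch also occurs in both product sections.

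**3. Lozenge precautions**

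The four bullets in 8.1.6 cover: non-smokers, occasional smokers and minors; skin hypersensitivity and allergy to nicotine or patch components; generalized skin disorders; and certain cardiac and cerebrovascular conditions. The four bullets in 8.2.6 are the same, so 4 of 4 match. The bullet on components still names the patch. Section 8.2.1 lists the lozenge's own inactive ingredients, aspartame among them, and none appears in the precaution list. The adverse-event list in 8.2.6, by contrast, is specific to the lozenge (hiccups and jaw pain, for example). The carry-over is therefore confined to the precautions and the shared general text.

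**The case against.** The case for leaving the text alone has four parts.

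**The smoking text can be read as a target with a fallback.** Section 8.1.4 first tells the patient to stop on quit day. It allows continued smoking only conditionally, and warns that doing so can increase adverse effects. Section 8.1.6 also concedes, in the same sentence as its reassurance, that overdose potential rises if the patient smokes. This largely stands: 8.1.6 and 8.1.7 do not disagree about the risk from cigarettes, and to call 8.1.4 and 8.1.7 opposites would be too strong. But the protocol never states the target-and-fallback reading, and 8.1.7 and 8.2.7 admit no exception.

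**The combined-use text could mean a small risk that is not significant.** That is possible, but the protocol does not say so.

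**Other materials may resolve it.** Decision trees, patient information sheets and weekly discussion of side effects with the principal investigators are all planned. The appendices and sheets are not in the text supplied, so one can assert neither that they cure the inconsistency nor that counselors and patients actually receive conflicting advice.

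**Lozenge ingredients are listed in 8.2.1, and the copied bullet retains nicotine allergy.** Both are true, but the precaution list still directs attention to the wrong product.

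A reader might also infer a consequence for safety reporting, because Section 5.5.2 calls an event unexpected when its type or "the severity of the event is NOT listed in the protocol (please refer to Section 8) or drug package insert". The documents do not support that step:

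- The package insert is an alternative reference, so Section 8 does not decide expectedness alone.
- Overdose signs are printed in 8.1.7 and 8.2.7 whichever statement on combined use one prefers. Whether a 7-day report is due therefore does not turn on which statement is read.
- The copied bullets describe populations, not events.

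**Conclusion.** The point holds as an internal inconsistency in three places: combined use (8.1.6 against 8.1.7, and 8.2.6 against 8.2.7), smoking during NRT (8.1.4 against 8.1.7, and 8.2.4 against 8.2.7), and the copied lozenge precautions in 8.2.6. The first and third are plain on the page. The second is milder, for the reason given above.

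It merits correction because it concerns operative instructions for the Arm B regimen. It is not a fault of design, and it leaves power, alpha and the analysis untouched.

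The documents do not say how many patients would use both products or smoke while on NRT. A reader might multiply the earlier trial's figures in Section 1.3.4, 0.80 x 0.83 = 0.66, and take about 66% as the share affected. That product measures uptake of any NRT, patch and/or lozenge, in a trial that also offered bupropion and varenicline. It measures neither combined use nor smoking on NRT, so no share is claimed here.

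The conclusion rests on the protocol text alone, without the decision trees, the patient sheets or the package inserts.

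**What to change.** At the next amendment the sponsor's medical and pharmacy leads should:

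1. Reconcile 8.1.4, 8.1.6 and 8.1.7, and likewise 8.2.4, 8.2.6 and 8.2.7, so that each product section carries one consistent statement on combined use and one on smoking during NRT.
2. Correct the copied precaution list in 8.2.6 so that it refers to the lozenge.
3. Check that the decision trees in Appendices VII and VIII agree with the reconciled text.

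The clinical content is for those leads to settle; this review proposes none. The cost is wording in an amendment already being made, plus a check of two appendices. No data collection, sample size or analysis changes.

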#### 8.1.7

#### Potential Interactions

There is increased risk of nicotine overdose in patients who continue smoking while using a nicotine replacement therapy, or those utilizing more than one form of nicotine replacement therapy. Caution should be used to prevent overdose, and smoking should be completely discontinued while using therapy.

Signs and symptoms of nicotine overdose may include:

abdominal or stomach pain, cold sweat, confusion, convulsions (seizures), disturbed hearing and vision, drooling, extreme exhaustion, pale skin, rapid heartbeat, and tremors. Contact your doctor if you experience any of these symptoms.

## 8.2 Nicotine Polacrilex Lozenge (NSC #741859)

### 8.2.1 Description

Nicotine Polacrilex Lozenges are a form of Nicotine Replacement Therapy that deliver nicotine to your body, temporarily relieving craving and nicotine withdrawal symptoms when you quit smoking. The lozenges are available in dose concentrations of 4mg or 2mg.

Depending on specific commercial product, may also contain the following inactive ingredients (not all inclusive): aspartame, calcium polycarbophil, flavor, magnesium stearate, mannitol, potassium bicarbonate, sodium alginate, sodium carbonate, xanthan gum. Please refer to commercial package insert" as necessary.

